## **12.2 INFORMED CONSENT REQUIREMENTS**

Before a subject is enrolled in the study, the Investigator or his/her designees must explain the purpose and nature of the study, including potential benefits and risks and all study procedures to the subject's parent/guardian. The subject's parent/guardian must sign and date an IRB/IEC-approved ICF prior to the conduct of any study-related activities. A copy of the signed consent form will be given to the subject's parent/guardian and the original will be retained in the study site's records.

## **12.3 INDEPENDENT ETHICS COMMITTEE/INSTITUTIONAL REVIEW BOARD**

Prior to study initiation at each site, the Investigator will obtain approval for the study from an appropriate IRB/IEC and provide the Sponsor with a copy of the approval letter. The IRB/IEC must also review and approve the study site's ICF and any other written information provided to the subject's parent/guardian prior to enrollment, as well as any advertising materials used for subject recruitment. Copies of the ICF and advertising materials must be forwarded to the Sponsor for review before submission to the IRB/IEC prior to the start of the study.

If, during the study, it is necessary to amend either the protocol or the ICF, the Investigator is responsible for obtaining IRB/IEC approval of these amended documents prior to implementation. Copies of the IRB/IEC correspondence and approval letters must be sent to the Sponsor.

During the conduct of the study, an annual progress report will be compiled by the Sponsor for submission to IRBs/IECs as required.

A written summary of the study will be provided by the Investigator to the IRB/IEC following study completion or termination according to the IRB or IEC standard procedures. Additional updates will also be provided in accordance with the IRB/IEC's standard procedures.

## **12.4 PRESTUDY DOCUMENTATION REQUIREMENTS**

Before the commencement of the clinical study, the following documents will be provided to the site: Investigators' Brochure, Protocol, ICF, Budget Agreement, and eCRF.

The site will be required to provide the following documents to United Therapeutics Corporation or designee prior to study start: Signature page of the protocol, Form FDA 1572, Financial Disclosure Form, IRB/IEC composition documentation, IRB/IEC protocol and informed consent approval letters, and Curriculum Vitae of study staff listed on the Form FDA 1572.

## **12.5 SUBJECT CONFIDENTIALITY**

Every effort will be made to keep medical information confidential. United Therapeutics Corporation, the FDA or other regulatory bodies, and the IRB/IEC governing this study may inspect the medical records of any subject involved in this study. The Investigator may release the subject's medical records to employees or agents of the Sponsor, the IRB/IEC or the FDA or appropriate local regulatory agencies for purposes of checking the accuracy of the data. A number will be assigned to all subjects and any report published will not identify the subject's name.

## **13 ADMINISTRATIVE AND LEGAL OBLIGATIONS**

### **13.1 PROTOCOL AMENDMENTS AND STUDY TERMINATION**

Protocol amendments that could potentially adversely affect the safety of participating subjects or that alter the scope of the investigation, the scientific quality of the study, the experimental design, dosages, duration of therapy, assessment variables, the number of subjects treated, or subject selection criteria may be made only after consultation between United Therapeutics Corporation or its designee and the Investigator.

All protocol amendments must be submitted to and approved by the appropriate regulatory authorities and IRB/IEC prior to implementation.

A report documenting study termination must also be submitted to and acknowledged by the appropriate IRB/IEC for each study site.

At the end of the study, where applicable, a final report will be provided to the local regulatory agencies.

### **13.2 STUDY DOCUMENTATION AND STORAGE**

In accordance with federal/national regulations, ICH, and GCP guidelines, the Investigator must retain study records for at least 2 years after the last approval of a marketing application in an ICH region and until there are no pending or contemplated marketing applications in an ICH region or at least 2 years have elapsed since the formal discontinuation of clinical development of the investigational product. The Investigator must notify United Therapeutics Corporation before any disposal or change in location of study records.

### **13.3 STUDY MONITORING AND DATA COLLECTION**

In accordance with federal/national regulations, ICH, and GCP guidelines, monitors for United Therapeutics Corporation or its designee will periodically contact the sites and conduct on-site visits. During these visits, the monitor will at a minimum: confirm ethical treatment of subjects, assess study progress, review data collected, conduct source document verification, verify drug accountability periodically, and identify any issues requiring resolution.

The Investigator agrees to allow the monitor direct access to all relevant documents and to allocate his/her time and his/her staff to the monitor to discuss any findings or any relevant issues.

## 15 APPENDICES

### 15.1 GUIDELINES AND DEFINITIONS FOR RECORDING ADVERSE EVENTS

The Principal Investigator or a designated member of his/her staff will probe each subject's parent/guardian for any adverse events (AEs) that may have occurred. The Investigator should always ask the same question when conducting the verbal probe in order to ensure uniformity between subjects. The Investigator should ask:

“How is the subject doing (feeling)?”

Based on the parent/guardian's response to this question, the Investigator should ask additional questions relevant to the specific complaint, such as:

“How severe is/was the symptom?”

“How often did the symptom occur?”

“How long did the symptom last?”

It is the Investigator's responsibility to review the results of all diagnostic and laboratory tests as they become available and ascertain if there is a clinically significant change from Baseline. If the results are determined to be a clinically significant change from Baseline, this should be reported as an AE. The Investigator may repeat the diagnostic procedure or laboratory test or request additional tests to verify the results of the original tests. When possible, a diagnosis associated with the abnormality should be used as the reported AE.

Using provided definitions, the Investigator will then:

1. Rate the intensity and seriousness of the AE
2. Estimate the causality of the AE to study drug
3. Note actions taken to counteract the AE.

Definitions of Intensity, Seriousness, Causality, and OutcomeINTENSITY

An assessment of the relative intensity (severity) of an AE should be based on the NCI-CTCAE, Version 5.0. The maximum intensity encountered during the evaluation period should be checked. The assessment of intensity should be independent of the assessment of the seriousness of the AE.

SERIOUSNESS

A serious adverse event (SAE) is one that represents an actual or potential significant hazard. This includes, but is not limited to, an event that is fatal, life-threatening, permanently or severely disabling, requires or prolongs inpatient hospitalizationa, is a congenital abnormality or is medically significant (important medical events that may not result in death, be life-threatening, or require hospitalization may be considered a SAE when, based upon appropriate medical judgment, they may jeopardize the subject and may require medical or surgical intervention to prevent 1 of the outcomes listed in this definition).

aHospitalizations that would not be considered SAEs include those for:

- Routine treatment or monitoring of the study indication not associated with any deterioration in condition.
- Treatment which was elective or preplanned, for a pre-existing condition not associated with any deterioration in condition (eg, preplanned operation which does not lead to further complications etc).
- Treatment of an emergency, in an outpatient setting for an event not fulfilling any of the definitions of serious as given above and not resulting in hospital admission.

CAUSALITY

An estimate of causality between a specified AE and the study drug is made by the Investigator. Several factors should be considered when determining causality. These factors include temporal relationship to the study drug.

- Definitions of the causality categories are as follows:
  - NOT RELATED – There is not a temporal relationship to study drug administration (too early, or late, or study drug not taken), or there is a reasonable causal relationship between another drug, or concurrent disease and the SAE, or any of the following:

- An event that precedes the first administration of study drug
- An event for which the cause is clearly related to an external event
- Temporal relationship to study drug is atypical
- Is readily explained by an intercurrent illness AND has an expected level of severity, duration, and resolution
- An alternative explanation (concomitant drug, intercurrent illness) is likely.
- POSSIBLE – There is a reasonable causal relationship between the study drug and the SAE, or any of the following:
  - Has a reasonable temporal relationship to study drug
  - The event has a plausible biological link to the activity of the study drug
  - Is unlikely to be related to an intercurrent illness or has an unexpected degree of severity, duration, or complication.
- PROBABLE – There is a reasonable causal relationship between the study drug and the SAE, or any of the following:
  - Has a reasonable temporal relationship to study drug
  - The event has a plausible biologic link to the activity of the study drug
  - Not readily explained by an intercurrent illness
  - Not readily explained by external event.

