**Table 3-2 Schedule of Times and Events – Long-term Outcome Phase**

Study Procedures	Long-term Outcome Phase	
Assessment Period	6 Months (Corrected Age) Phone Contact a	1 Year (Corrected Age) Visit b
Study Day	Calculated	Calculated
Visit Window	±2 weeks	±4 weeks
Weight, Length, and Head Circumference		X
Serious Adverse Reactions c	X	X
Assessment of General Health	X	X

Abbreviations: PMA, postmenstrual age

a To be performed at 6 months corrected age for all subjects, as possible, including those discharged from the hospital prior to 40 Weeks PMA. See Section [7.5](#).

b To be performed at 1 year corrected age for all subjects, as possible, including those discharged from the hospital prior to 40 Weeks PMA. See Section 7.5.

c Refer to Section [9.1.3](#) for the definition of serious adverse reactions.

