### **9.1.3      Serious Adverse Reaction**

A SAR is a SAE occurring at any dose that is assessed by the Investigator as possibly or probably related to the CSM. During the Long-term Outcome Phase of the study, only SARs will be reported to United Therapeutics Global Drug Safety according to Section 9.4. Other conditions that will be evaluated as part of the study endpoints are therefore not subject to expedited reporting.

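### Do the overlapping causality categories in Protocol 15.1 leave serious events uncaptured in the Long-term Outcome Phase, so that the plan has to change?

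*Protocol*

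**What the plan says.** **Causality (Protocol 15.1).** The investigator rates each event NOT RELATED, POSSIBLE or PROBABLE. NOT RELATED begins "There is not a temporal relationship to study drug administration (too early, or late, or study drug not taken", and its further criteria include "An alternative explanation (concomitant drug, intercurrent illness) is likely". POSSIBLE and PROBABLE share the opening "There is a reasonable causal relationship between the study drug and the SAE, or any of the following", and both lists contain "Has a reasonable temporal relationship to study drug". The section leaves the weighing to judgement: "Several factors should be considered when determining causality".

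**What is followed long term.** Protocol 9.1.3 defines a SAR as a serious adverse event (SAE) "assessed by the Investigator as possibly or probably related to the CSM", and adds: "During the Long-term Outcome Phase of the study, only SARs will be reported to United Therapeutics Global Drug Safety". Table 3-2 has one adverse-event row, "Serious Adverse Reactions", next to general health at both contacts and growth at 1 year. Sections 3.3.2 and 7.5 also name SARs for this phase. Section 3.3.2.4 ends adverse event documentation at the 40 Weeks PMA/Hospital Discharge assessments.

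**General rules.** Protocol 9.2 requires AEs and SAEs during the study to be documented in the eCRF. Section 9.4 has sites enter SAEs whatever their causality. Neither is limited by phase.

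**Analysis.** SAP 1.1 reports early termination with 3 randomized subjects and restricts output to listings. SAP 8 lists all eCRF data, SAP 11.2 lists AEs with no causality filter, SAP 10.3 lists every general-health answer, and SAP 11.3 lists deaths.

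**The concern.** A causality rating normally annotates an event that is already in the database, so a reader can see the rating and disagree with it. Under the long-term schedule the rating appears to work as an entry filter: a serious event rated POSSIBLE or PROBABLE is a SAR and is captured, while one rated NOT RELATED may leave no row in Listing 16.2.7.2. Because the categories overlap and no precedence is given, two investigators could read the same definitions, rate the same event differently, and both comply. NOT RELATED can also be met because an event is late, and neither document says what late means after a single infusion.

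Long-term outcome is a secondary objective, and Protocol 1.2 says that UNEX-42 had not been evaluated clinically. If a non-fatal serious event were left out, nobody could reassess the judgement, and the absence of late rows might be taken to mean that no SAE occurred. Sections 9.2 and 9.4 add doubt, because read alone they require entry of the events that Table 3-2 does not ask about.

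**Working it through.** **1. The plan's own timing.** Inputs: gestational age at birth 23w0d (161 days) to 26w6d (188 days) and postnatal age 3 to 14 days at randomization (Protocol 4.1); 40 weeks = 280 days.

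- Earliest: 280 − 188 − 14 = 78 days.
- Latest: 280 − 161 − 3 = 116 days.

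These match the 78 to 116 in Table 3-1. Also 17 + 52 = 69 weeks, the maximum duration in Protocol 3.6.

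**2. Length of the SAR-only period.** One year of corrected age is 364 days after 40 weeks PMA.

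- 6-month contact: 78 + 182 = Day 260 to 116 + 182 = Day 298.
- 1-year visit: 78 + 364 = Day 442 to 116 + 364 = Day 480.
- Share: 364/480 = 75.8% to 364/442 = 82.4%.
- With the ±4-week visit window: (364 − 28)/(480 − 28) = 74.3% to (364 + 28)/(442 + 28) = 83.4%.
- If discharge is assumed at 36 weeks PMA: (364 + 28)/480 = 81.7% to (364 + 28)/442 = 88.7%. So 82% is not an upper limit.

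This measures planned time. The documents give no rate of late serious events and no rate of disagreement between raters, so the number of affected events cannot be derived.

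**3. Which overlap matters.** Let T be reasonable timing and A a likely alternative explanation. A alone meets NOT RELATED. T alone meets both POSSIBLE and PROBABLE. An event with T and A therefore meets all three. Letting four further facts vary freely (external event, intercurrent illness, biological link, unexpected severity) gives 2^4 = 16 profiles, and all 16 meet all three categories. That is true by construction and says nothing about frequency. POSSIBLE and PROBABLE both count as SARs, so the wording they share in "There is a reasonable causal relationship between the study drug and the SAE, or any of the following" cannot change whether an event qualifies. Only the boundary with NOT RELATED can.

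**4. Which events are exposed.** Taking the sections together:

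- SAEs that begin in the Post-treatment Phase are entered whatever their rating (9.4) and followed to resolution, death or loss to follow-up (3.3.2.4, 9.3). They are not affected.
- Deaths are listed without regard to causality up to the end of study, but SAP 11.3 limits this to 4 weeks after infusion for subjects who terminate prematurely.
- Non-fatal serious events starting in the long-term phase and rated NOT RELATED are exposed. They may still appear in the general-health answers; the script's questions are not in the documents.

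**5. Effect on output.** Two contacts for each of 3 infants gives at most 6 contacts. No incidence is computed. An SAE that is entered appears in the listing whatever its rating.

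**The case for a change.** The strongest case for acting is that the documents conflict on collection. A site that learns at the 1-year visit of a hospital admission it considers unrelated can cite 9.2 and 9.4 for entering it, and 3.3.2.4, 9.1.3 and Table 3-2 for leaving it out. The SAP cannot settle this, since it lists only what was entered. In a listings-only report each row is the evidence, and no summary would reveal a missing one. The death listing is also a weaker safeguard than it looks, given its 4-week limit and the fact that sponsor termination, which happened, is a stated reason for withdrawal. Two remedies suggest themselves: enter every long-term SAE while safety reporting stays limited to SARs, or add a footnote saying what was collected.

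The mismatch and the overlap both stand. The case for a change does not.

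- The four places that address the phase directly (3.3.2, Table 3-2, 7.5 and 9.1.3) all name SARs. Reading the specific provisions as governing the general ones is the natural way to run the study. Wanting all SAEs instead is a different design preference, with costs in parental recall over several months and extra data entry.
- Full entry cannot simply be separated from safety reporting. Under 9.4 an SAE entered electronically passes automatically to the sponsor's safety database, so that section would need rewriting too. These are protocol changes, and Protocol 13.1 requires regulatory and ethics approval before they take effect. That is a heavy step for a terminated study.
- An instruction in the SAP to list such events whatever their rating would repeat SAP 8 and 11.2.
- A footnote would be harmless, but it would disclose only what Table 3-2 already shows. The SAP plans one AE listing with no separate long-term section that could stand empty and mislead.

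**Conclusion.** The concern is correct on the text but calls for no change. NOT RELATED can overlap with POSSIBLE and PROBABLE, and 9.2 and 9.4 were not worded to match the SAR-only long-term schedule. It would go too far to say that only SARs are collected, or that the rating decides whether an event is recorded at all: general health and growth are collected as well, and 9.2 and 9.4 read literally require entry. What remains is that the rating may decide whether a non-fatal serious event starting after 40 Weeks PMA/Hospital Discharge is captured as a safety event.

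The SAR-only period is 76% to 82% of planned follow-up if infants stay in hospital to 40 weeks PMA, and about 82% to 89% if discharge is assumed at 36 weeks PMA. In the study as it ended, this concerns at most 6 contacts in 3 infants and no computed result. SAR-only follow-up long after a single infusion is a fair trade-off, and the general wording elsewhere is a drafting slip.

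This conclusion assumes that the report stays listings-only, as SAP 1.1 states, and that its readers consult Table 3-2 before drawing anything from the absence of late SAEs. If long-term SAE incidence were to be summarized or compared, the point would carry more weight.

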### OUTCOME

- Fatal – the study subject died.
- Not Recovered/Not Resolved – the AE was ongoing at the time of death or at the time the subject was lost to follow-up.
- Recovered/Resolved – the AE resolved.
- Recovered/Resolved with Sequelae – the AE is considered resolved; however, there are residual sequelae. Some events do not return to baseline, such as metastasis or progression of disease; however, once these events are determined by the Investigator to be stable or chronic, the Investigator may consider the event to be resolved or resolved with sequelae.
- Recovering/Resolving – the AE is improving but is not yet completely recovered/resolved.
- Unknown – the outcome of the AE cannot be determined.

**ABBREVIATIONS AND DEFINITIONS**

AE	Adverse event
ATC	Anatomical Therapeutic Chemical
BPD	Bronchopulmonary dysplasia
eCRF	Electronic Case Report Form
GA	Gestational age
IV	Intravenous
PMA	Postmenstrual age

## 1 PREFACE

This Statistical Analysis Plan provides further details of the planned analyses for Study UNX-BP-101, as presented in the study protocol.

### 1.1 CHANGES TO PLANNED ANALYSES

This study was terminated early by United Therapeutics Corporation. The first dose cohort was partially enrolled with 3 subjects randomized prior to study termination. Therefore, only listings will be provided. No summary or inferential analyses will be provided.

## 2 STUDY OBJECTIVES AND ENDPOINTS

### 2.1 OBJECTIVES

#### 2.1.1 Primary Objective

To assess the safety and tolerability of intravenous (IV) infusion of UNEX-42 in infants born at <27 weeks of gestational age (GA) and exhibiting respiratory distress.

#### 2.1.2 Secondary Objectives

To assess the effect of UNEX-42 on the following:

1. Incidence and severity (mild, moderate, severe) of bronchopulmonary dysplasia (BPD) or death at 36 weeks postmenstrual age (PMA)
2. Short-term outcomes including oxygen utilization and ventilation exposure in the first 28 days after treatment.
3. Long-term outcomes up to 1 year corrected age.

### 2.2 ENDPOINTS

#### 2.2.1 Primary Endpoints

The primary endpoints are the following safety assessments during the Post-treatment Phase:

- Incidence of treatment-emergent adverse events (AEs)
- Incidence of all-cause mortality through Week 36 PMA
- Incidence of treatment-related AEs
- Absolute and changes from Baseline in laboratory parameters
- Absolute and changes from Baseline in vital signs

## 2.2.2 Secondary Endpoints

[figure not shown]
The secondary endpoints are the following assessments:

- Incidence of BPD or death at 36 weeks PMA
- Severity of BPD (mild, moderate, severe) at 36 weeks PMA
- Complications of prematurity during the Post-treatment Phase (diagnosis of sepsis, pneumothorax, clinically significant patent ductus arteriosus requiring treatment or ligation, necrotizing enterocolitis requiring treatment or surgery, intraventricular hemorrhage [including highest grade], periventricular leukomalacia, and retinopathy of prematurity [including stage])

## 3 STUDY DESIGN

This is a multicenter, placebo-controlled, randomized, dose escalation, safety, and tolerability study of UNEX-42 in infants born at <27 weeks of GA at high risk for BPD. UNEX-42 will be administered via IV infusion to 3 cohorts at 20, 60, and 200 pmol phospholipid/kg body weight. Within each cohort, eligible subjects will be randomly assigned to receive either UNEX-42 or placebo treatment (2:1 allocation ratio). A schematic presentation of the study design is presented in [Figure 3-1](#).

**Figure 3-1 Schematic of Study Design for an Individual Subject**

\*Subjects that discontinue the study prematurely should have the 40 Weeks Postmenstrual Age/Hospital Discharge assessments performed if possible. Subjects that complete the 40 Weeks PMA Assessment or are discharged from hospital will continue into the Long-term Outcome Phase.

Study assessments will occur during the study at the following time points: Screening, Baseline, 24 and 72 hours postdose, 7 days postdose, weekly until 35 weeks PMA, 36 weeks PMA, and 40 weeks PMA/hospital discharge during the Post-treatment Phase. For subjects that complete the Post-treatment Phase, the Long-term Outcome Phase will occur at 6 months (phone contact) and 1 year of corrected age (site visit).

